	
Safety data:
 
Staff will record information about immediate (within 30 minutes) AEs after each injection.
 
Subjects will record in a DC information about solicited injection site reactions occurring up to 7 days after each injection, solicited systemic reactions occurring up to 14 days after each injection, and unsolicited AEs occurring up to 28 days after each injection. Information on SAEs will be reported throughout the study and serious and non-serious AESIs will be collected in defined time windows according to the type of AESI.
 
DCs will also be provided to the subjects to collect information on SAEs in-between injections (from 28 days post-injection until the next injection). Finally, a memory aid (MA) will be provided to collect information on SAEs during the safety follow-up (from 28 days after the last injection until 6 months after the last injection).
 
Staff will review the safety data with the subjects during post-vaccination visits.

Duration of Participation in the Study:
	
The expected duration of each subject's participation in the study is approximately 18 months, including a safety follow-up period of 6 months post last vaccination.
 
Subjects who are dengue-positive by rapid diagnostic test (RDT) or dengue IgG ELISA at Screening Visit and negative by PRNT (sample collected before the first injection [at Visit 1] and assayed before second injection) will be considered as not previously exposed. Therefore, they will not receive any further injections and will be followed for safety until 6 months after the last dose. In addition, if they received the vaccine, provisions for timely access to medical care will be offered for 10 years after the last dose, according to IDMC prior recommendations.

Investigational Products
 
Study Product:
 
Form:
 
Composition:
 
Route:
 
Batch Number:
	
CYD Dengue Vaccine
 
Powder and solvent for suspension for injection
 
Each individual 0.5 mL dose of reconstituted tetravalent vaccine contains:
 
 • 4.5-6.0 log10 cell-culture infectious dose 50% (CCID50) of each live, attenuated, dengue serotype 1, 2, 3, 4 virus • Excipients: essential amino acids, non-essential amino acids, L-arginine chlorhydrate, saccharose, D-trehalose dihydrate, D-sorbitol, Tris (hydroxymethyl) aminomethane, and urea • Solvent: NaCl 0.4% 
Subcutaneous (SC)
 
To be determined

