All acute febrile illness with diagnosis of dengue requiring hospitalization within the first 5 days after fever onset, occurring after the first visit (V01) and until the end of the 6-month safety follow-up														

Visit (V) and Phone Call (PC) Number	Scr. *	V01*	V02	V03	V04	V05	PC1	PC2	V06	V07	PC3	PC4	V08	6-month Follow-up†
Trial Timelines Injection (Inj); Day (D); Month (M)	-D28 to – D0	Inj 1 (D0)	Inj 1 +7D	Inj 1 +14D	Inj 1 +28D	Inj 2 (M6)	Inj 2 +7D	Inj 2 +14D	Inj 2 +28D	Inj 3 (M12)	Inj 3 +7D	Inj 3 +14D	Inj 3 +28D	Last Inj +6 months
Time Windows (Days)		+3	+3	+14	±20	+3	+3	+14	±20	+3	+3	+3	+14	+30
Injection		Inj. 1				Inj 2				Inj 3				
30-Min. Observation Period – Collection of immediate events		X				X				X				
Injection Site Reactions & Systemic Events Assessment		Solicited injection site reactions will be collected for Days 0–7 after each injection. Solicited systemic reactions will be collected for Days 0–14 after each injection. Unsolicited events will be collected for Days 0–28 after each injection.												
Diary Card (DC) §§§ Provided Checked Collected		DC1	DC1	DC1	DC2 DC1 DC1	DC3 DC2 DC2			DC4 DC3 DC3	DC5 DC4 DC4			DC5 DC5	
Memory Aid (MA) §§§ Provided														MA
Termination Record****														X
SAEs and Serious AESIs ††††	††††	SAEs from the first visit (V01) and until the end of the 6-month safety follow-up; AESIs in defined time windows according to the type of AESI												

* Serology, hematology and biochemistry results, as well as all other information collected as part of the screening of potential subjects will be captured in the source document. Inclusion/exclusion criteria, significant medical history, history of dengue infection/vaccination, of YF infection/vaccination, and of Zika infection, physical/clinical examinations, CD4 count and HIV viral load results will be captured in the CRF at V01 for eligible subjects. The Screening Visit and Visit 1 can be simultaneous for subjects tested positive by RDT and whose tests have been performed in appropriate time windows (within 4 weeks before injection for hepatitis serology, hematology, and biochemistry; within 2 months for CD4 count and HIV viral load) as part of the subject's routine follow-up.

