Safety data will be collected following each injection. Clinical site personnel will record immediate AEs that occur within the 30 minutes after injection. Subjects will record in the diary card (DC) information about solicited injection site reactions from D0 to D7 post-injection, about solicited systemic reactions from D0 to D14 post-injection, and unsolicited AEs occurring up to 28 days post-injection. Information on SAEs will be reported throughout the study (See [Section 10.1](#) and Operating Guidelines for more information). Serious and non-serious AEs of special interest (AESIs) will be collected in defined time windows according to the type of AESI.

DCs will be provided to subjects to collect information on SAEs in-between injections (ie, from 28 days to 6 months post-Inj 1; and from 28 days to 6 months post-Inj 2) A memory aid (MA) will be provided to subjects to help them record SAEs during the 6 months safety follow-up (from 28 days post-Inj 3 to 6 months after last injection). Subjects are to contact the Investigator (within the first 5 days after fever onset) in case of hospitalization for suspected dengue disease at any time during the study for virological confirmation of the disease.

Clinical site personnel will review the safety data with the subjects during post-injection visits.

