5.5 Interruption of the Study

The detection/fulfillment of the following safety signals will put the study on a temporary hold:

- With regard to investigational products:

- 15% of the total subjects included in the study** experience a Grade 3 solicited systemic reaction occurring within 14 days after any study injection and persisting for at least 48 hours and judged as related to the vaccination by the Investigator and not explained by any other possible etiology.

and/or

- 3 SAE (including serious AESI) considered as related to the vaccination by the Investigator or the Sponsor, except for the SAEs corresponding to the HIV condition included below.

- With regard to HIV condition:

- **In 20% of the total subjects included in the study:** Confirmed plasma HIV-1 RNA > 1000 copies/mL 28 days post-injection after having been undetectable (< 50 copies/mL) pre-injection, not explained by non-adherence to ART and not explained by any other possible etiology.

or

- **In 10% of the total subjects included in the study:** Confirmed decrease in CD4 count greater than 30% assessed 28 days post-injection compared to the pre-injection value, not explained by non-adherence to ART and not explained by any other possible etiology.

It is to be noted that any case of an increase in HIV-1 RNA > 1000 copies/mL or decrease in CD4 count greater than 30% observed 28 days post-injection, not explained by non-adherence to ART and not explained by any other possible etiology, will be considered as an SAE. This increase in HIV viral load or decrease in CD4 count will be considered as “confirmed” if a second test taken 4 weeks after the first (ie, approximately 2 months post-injection) shows the same value/trend. The IDMC will be immediately notified if either or both criteria occur in any of the subjects enrolled in the study.

The IDMC will also be immediately notified when the percentage of subjects defined in one of the 4 safety signals described above has been reached. The IDMC will then assess and recommend in an expedited way whether study enrollment and injections can continue, and/or whether other actions should be completed. In this scenario, additional biological tests may be required to assess the evolution of the subjects and to decide on the study continuation.

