9.1.1.2 Safety Endpoints

The primary endpoints for the evaluation of safety are:

- Occurrence of any unsolicited systemic AE reported within 30 minutes after each injection
- Occurrence of solicited (ie, pre-listed in the subject's DC and in the CRB) injection site reactions (pain, erythema, and swelling) occurring up to 7 days after each injection
- Occurrence of solicited systemic reactions (fever, headache, malaise, myalgia, and asthenia) occurring up to 14 days after each injection
- Occurrence of unsolicited AEs occurring up to 28 days after each injection
- Occurrence of serious and non-serious AESIs in defined time windows according to the type of AESI
- Occurrence of SAEs throughout the trial (ie, from D0 through the end of the study)
- Occurrence of hospitalized VCD cases throughout the study (ie, from D0 through the end of the study)

Other endpoints will be recorded or derived as described in the Statistical Analysis Plan. Depending on the item, these could include: nature (Medical Dictionary for Regulatory Activities [MedDRA] preferred term), time of onset, duration, number of days of occurrence, Grade of severity, relationship to vaccine, action taken, whether the event/reaction led to early termination from the study, seriousness, or outcome.

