9.1.1.3.2 Reactogenicity (Solicited Reactions From Day 0 to Day 7/D14 After Each Vaccination)

After the first vaccination, subjects will be provided with a diary card, a digital thermometer, and a flexible ruler, and will be instructed how to use them. The following items will be recorded by the subjects in the diary card on the day of vaccination and for the next 7 days (ie, D0 to D7) until resolution:

- Daily temperature, with the route by which it was taken
- Daily measurement or intensity Grade of all other solicited injection site and systemic reactions
- Action taken for each event (eg, medication)

The action(s) taken by the subject to treat and/or manage any **solicited reactions** will be classified in the CRB using the following list (all applicable items should be checked):

- None
- Medication
- Health care provider contact
- Hospitalized
- Discontinuation of study vaccination

[Table 9.1](#) and [Table 9.2](#) present, respectively, the injection site reactions and systemic reactions that are pre-listed in the diary cards and CRB, together with the intensity scales.

Table 9.1: Solicited injection site reactions: terminology, definitions, and intensity scales

CRB term (MedDRA lowest level term [LLT])	Injection site pain	Injection site erythema	Injection site swelling
Diary card term	Pain	Redness	Swelling
Definition	Pain either present spontaneously or when the injection site is touched or injected limb is mobilized	Presence of a redness including the approximate point of needle entry	Swelling at or near the injection site Swelling or edema is caused by a fluid infiltration in tissue or cavity and, depending on the space available for the fluid to disperse, swelling may be either soft (typically) or firm (less typical) to touch and thus can be best described by looking at the size of the swelling

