11.1 Data Collection and CRB Completion

Individual diary cards, specifically designed for this study by the Sponsor and provided to the study sites, will be given to study participants for the recording of daily safety information as described in [Section 9.1.1.3](#). These diary cards will include pre-listed terms and intensity scales (see [Table 9.1](#) and [Table 9.2](#)) as well as areas for free text to capture additional safety information or other relevant details. Subjects will also be provided with rulers for measuring the size of

injection site reactions, and with standard digital thermometers for measuring daily temperatures. To ensure consistency of reporting, the study sites will instruct subjects on how to correctly use these tools.

The 6-month follow-up will be done by interviewing subjects either during a Visit or over the telephone using a questionnaire to capture SAEs and AESIs, if applicable. A MA will be provided to the subjects at the preceding study Visit to help them record information on events occurring between this Visit and the 6-month follow-up. In case a follow-up Visit is planned, a diary card may be provided to the subject.

Relevant information will be transcribed into the AE CRF. Any SAEs captured during this 6-month follow-up period will be reported and followed-up as per the normal process for reporting SAEs.

At specified intervals, the Investigator or an authorized designee will interview the subjects to collect the information recorded in the diary card, and will attempt to clarify anything that is incomplete or unclear. All clinical study information gathered by the study site will be reported electronically by the Investigator or authorized designee using a web-based CRB. (Any information that was not documented in the diary card will first be captured in the source document and then reported electronically.) The CRB has been designed specifically for this study under the responsibility of the Sponsor, using a validated Electronic Records / Electronic Signature-compliant platform (21 CFR Part 11).

To ensure the correct and consistent completion of the CRBs, the Sponsor or authorized representative will provide all necessary tools, instructions, and training to all site staff involved in data entry prior to study start. Additional instructional documents such as training manuals and completion instructions will be provided to assist with data entry during the course of the study.

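### Protocol 9.1.1.3.2 has subjects record temperature and solicited systemic reactions for D0–D7 only, while the study plan, primary endpoint, hold criterion and SAP all use D0–D14

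*Protocol*

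**What the plan says.** Section 9.1.1.3.2 of the protocol, on how reactogenicity is assessed, has subjects make diary entries "on the day of vaccination and for the next 7 days (ie, D0 to D7) until resolution". The items listed are daily temperature with its route, "Daily measurement or intensity Grade of all other solicited injection site and systemic reactions", and the action taken. No second window is given for systemic reactions, although the section heading mentions both Day 7 and Day 14. Section 11.1 says the diary cards are "given to study participants for the recording of daily safety information as described in" Section 9.1.1.3, which contains this text.

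Elsewhere the systemic window is 14 days:

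- Section 5.1.3, on what subjects enter in the diary card: "about solicited systemic reactions from D0 to D14 post-injection".
- Synopsis, safety data: "solicited systemic reactions occurring up to 14 days after each injection".
- Table of Study Procedures: "Solicited systemic reactions will be collected for Days 0–14 after each injection".
- Primary endpoint, Section 9.1.1.2: "Occurrence of solicited systemic reactions (fever, headache, malaise, myalgia, and asthenia) occurring up to 14 days after each injection".
- Hold criterion, Section 5.5: "Grade 3 solicited systemic reaction occurring within 14 days after any study injection".
- Protocol Section 12.1.1.2 and SAP Sections 3.2, 4.4.1, 4.4.1.1.4, 4.4.1.1.5 and 5.1.1.2 also use D0–D14 for systemic reactions. Where these sections give an injection site window, it is D0–D7.

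**The concern.** The protocol gives two diary instructions that disagree, and one of them stops a week before the primary endpoint window closes. The words on continuing until resolution protect a reaction already present by D7. They do nothing for one that begins on D8–D14. If a site or the printed card followed 9.1.1.3.2, that reaction would have no prompted daily record, and only the free space for other medical events up to D28 could catch it. It would then be an unsolicited event, with three consequences:

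1. **Causality and the early safety review.** By convention solicited systemic reactions count as related (Section 9.1.1.3.5). An unsolicited systemic event needs the Investigator's judgment. The early review of the first 20 subjects takes unsolicited events only if they were reported as related (Section 5.1.6), apart from SAEs and AESIs.
2. **Hold criterion.** Section 5.5 counts Grade 3 *solicited* systemic reactions within 14 days. An event filed as unsolicited does not meet those terms.
3. **Primary analysis.** The event would be missing from the D0–D14 systemic reaction rate and from the SAP's D8–D14 onset class.

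Fever is the most exposed item. It is graded from recorded temperatures, so a 14-day fever endpoint needs temperatures through D14.

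**Working it through.** **Step 1: compare the windows.**

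| Place | Systemic reactions | Injection site reactions |
|---|---|---|
| Protocol 9.1.1.3.2, body text | D0–D7 | D0–D7 |
| Protocol 9.1.1.3.2, heading | D7/D14, not assigned to a type | D7/D14, not assigned to a type |
| Protocol synopsis; Table of Study Procedures; 5.1.3; 9.1.1.2; 12.1.1.2 | D0–D14 | D0–D7 |
| Protocol 5.5 (hold criterion) | within 14 days | not used |
| SAP 3.2; 4.4.1; 4.4.1.1.4; 4.4.1.1.5; 5.1.1.2 | D0–D14 | D0–D7 |

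Only the body text of 9.1.1.3.2 applies D7 to systemic reactions as an instruction. The definitions in Section 9.1.1.1 also use headache on D0–D7, but only as a generic example.

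**Step 2: count the daily records.** D0–D7 is 8 days and D0–D14 is 15. The gap is 15 − 8 = 7 days per injection, and 7/15 = 47% of the endpoint window has no instructed recording for a reaction not already present.

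**Step 3: can the analysis recover a misfiled event?** SAP 4.4.1 defines an unsolicited AE by the CRF page on which it was recorded. SAP 4.4.1.1.1 to 4.4.1.1.4 derive the presence and onset of a solicited reaction from daily intensities. SAP 4.4.1.2.1 deals with measurable unsolicited events whose term is on the solicited list, but it only borrows the intensity scale and does not reclassify them. No SAP rule moves the event back, so with no daily record there is no solicited presence. If 9.1.1.3.2 were followed literally throughout, the D8–D14 onset class would be empty.

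**Step 4: weight of each affected subject.** Planned group sizes are 100 (vaccine) and 50 (placebo). Take a subject whose only systemic reaction after an injection starts on D8–D14 and is filed as unsolicited, and assume the subject stays in the denominator:

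- vaccine: 1/100 = 1.0 percentage point off that injection's rate;
- placebo: 1/50 = 2.0 percentage points.

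**Step 5: hold criterion.** If the denominator is the planned 150, then 0.15 × 150 = 22.5, so 23 subjects are needed. Grade 3 reactions filed as unsolicited would not count toward the 23.

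The number of D8–D14 onsets cannot be projected, because the documents give no onset distribution. The sample-size statement does not depend on this point.

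**The case against.** The strongest reply is that the intended window is not in doubt. The section's own heading mentions D14, Section 5.1.3 states the diary instruction with D14, and the SAP has a category of 15 days of occurrence, which suggests that data capture was designed for 15 days. Section 11.1 points to the whole of 9.1.1.3, not to the one sentence. SAP 4.4.1 also defines a solicited systemic reaction as a pre-listed event occurring within 0 to 14 days, so a headache on D10 is solicited by definition. Site staff interview the subject at the day-14 visit after injection 1 and telephone at day 14 after injections 2 and 3, and a blinded data review precedes database lock. The hold criterion already requires the Investigator to judge the reaction related, and it also requires Grade 3 and at least 48 hours' persistence. The trial is descriptive, with no hypothesis tested.

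Much of this stands. It shows which window was meant and makes harm less likely, and the causality convention does not affect the hold criterion. It does not remove the conflicting instruction. The SAP definition does not help when presence is computed from daily records that were never prompted. The day-14 calls remind subjects to record AEs, but the diary is checked and collected only at the 28-day visit. A descriptive trial still reports these rates as a primary result.

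**Conclusion.** The protocol is wrong as written on this point. Its assessment section gives one diary window, D0–D7, for temperature and solicited systemic reactions, and this conflicts with the D0–D14 window used by the endpoint, the hold criterion and the analysis. As written, 7 of the 15 days lack prompted recording for new-onset reactions. Whether data would be lost depends on the printed card, the CRF and site practice, none of which can be seen here. The possible error in the systemic reaction rates runs toward under-counting; its total size is unknown. The per-subject figures assume the planned group sizes and that affected subjects stay in the denominator; the 23-subject figure assumes a denominator of 150. The correction should be made because it touches a primary endpoint and a safety trigger and costs almost nothing.

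**What to change.** Reconcile the sentence in Section 9.1.1.3.2 with the windows stated elsewhere: injection site reactions recorded daily on D0–D7, temperature and the other solicited systemic reactions recorded daily on D0–D14, and either continued to resolution if still present when its window ends. Check that the three post-injection diary cards (DC1, DC3 and DC5) carry temperature and systemic reaction grids through D14. Optionally, change the headache examples in Section 9.1.1.1 to D14 and D15 so that they match this trial.

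The cost is a one-sentence protocol clarification and a diary-card check. No visit or call is added, because a contact at day 14 after each injection is already planned.

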9.1.1.3.3 Unsolicited Adverse Events

In addition to recording solicited reactions, subjects will be instructed to record any other medical events that may occur during the 28-day period after each injection. Space will be provided in the diary card for this purpose.

Information on SAEs will be collected and assessed throughout the study. SAEs related to study procedures and occurring between the Screening Visit and the first injection visit (V01), if applicable, will be first reported using a paper SAE Reporting Form, and then reported in the CRB for enrolled subjects. SAEs occurring from V01 until 6 months after the last injection will be directly reported in the CRB of subjects. Any SAE occurring at any time during the study will be reported by the Investigator in the CRB according to the completion instructions provided by the Sponsor; this includes checking the “Serious” box on the AE CRF and completing the appropriate Safety Complementary Information CRFs. All information concerning the SAE is to be reported either as part of the initial reporting or during follow-up reporting if relevant information became available later (eg, outcome, medical history, results of investigations, copy of hospitalization reports, and verbal autopsy questionnaire if used.). See [Section 10](#) for further details on SAE reporting.

For each unsolicited AE (whether serious or non-serious), the following information is to be recorded:

- Start and stop dates^a
- Intensity of the event:

For measurable unsolicited AEs that are part of the list of solicited reactions, the size of the AE as well as the temperature for fever will be collected and analyzed based on the corresponding scale used for solicited reactions (see [Table 9.1](#) and [Table 9.2](#)).

All other unsolicited AEs will be classified according to the following intensity scale:

- Grade 1: A type of AEs that is usually transient and may require only minimal treatment or therapeutic intervention. The event does not generally interfere with usual activities of daily living.

^a The stop date of all related AEs will be actively solicited. For other events, the investigator will provide the stop date when it becomes available. AEs for which no stop date was obtained during the course of the study will be considered as ongoing at the end of the study.

- Grade 2: A type of AEs that is usually alleviated with additional therapeutic intervention. The event interferes with usual activities of daily living, causing discomfort but poses no significant or permanent risk of harm to the research participant.
- Grade 3: A type of AEs that interrupts usual activities of daily living, or significantly affects clinical status, or may require intensive therapeutic intervention.
- Whether the AE was related to the investigational product (for unsolicited systemic AEs)
The Investigator will assess the causal relationship between the AE and the investigational product as either “Not related” or “Related”, as described in [Section 9.1.1.3.5](#).
- Action taken for each AE (eg, medication)
The action(s) taken by the subject to treat and/or manage any unsolicited AEs will be classified in the CRB using the following list (all applicable items should be checked):
 - None
 - Medication
 - Health care provider contact
 - Hospitalized
 - Discontinuation of study vaccination
- Whether the AE was serious
For each SAE, the Investigator will complete all seriousness criteria that apply (outcome, elapsed time, and relationship to study procedures)
- Whether the AE caused study discontinuation

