4.4.1.2.4 Duration

Duration is derived from the start and stop dates of the unsolicited AE provided in the clinical database:

- stop date of unsolicited AE – start date of unsolicited AE + 1.

The duration should be considered as missing only if one or both of the start and stop dates of the unsolicited AE is missing or partially missing.

Duration will be displayed by period as follows: 1-3 days, 4-7 days, 8-14 days, 15 days or more, Missing.

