5.3.1.5 Start Date and Stop Date

Missing or partially missing start dates for unsolicited AEs will remain missing and not be imputed. If the start is missing or partially missing, the time of onset will be considered to be missing. Nevertheless, unsolicited AEs with missing time of onset will be included in analyses according to the visit number collected in “Appeared after visit” or similar field. If either the start date or end date is missing or partially missing, the duration will be considered missing.

Missing or partially missing stop dates for AEs (solicited reactions and unsolicited AEs) will remain missing and not be imputed.

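### The SAP's duration tables have no 'ongoing' level, so events known to persist sit in 'Missing' with events of unknown duration and the longest-duration rows are only lower bounds

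*Protocol*

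**What the plan says.** **Protocol.** The footnote on stop dates in 9.1.1.3.3 has three parts. For related events, "The stop date of all related AEs will be actively solicited". Otherwise, "For other events, the investigator will provide the stop date when it becomes available". Finally, "AEs for which no stop date was obtained during the course of the study will be considered as ongoing", with the study's end as the reference point. Protocol 12.3.1 separately rules out replacement of missing safety data.

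**SAP, unsolicited AEs.** Section 4.4.1.2.4 defines duration as "stop date of unsolicited AE – start date of unsolicited AE + 1" and adds: "The duration should be considered as missing only if one or both of the start and stop dates of the unsolicited AE is missing". A partial date is treated the same way. The display rows are 1-3, 4-7, 8-14, 15 or more days, and Missing. Section 5.3.1.5 confirms: "Missing or partially missing stop dates for AEs (solicited reactions and unsolicited AEs) will remain missing and not be imputed".

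**SAP, solicited reactions.** Section 4.4.1.1.6 derives an overall number of days for a reaction still ongoing when the solicited period ends. If the stop date is absent or incomplete, that number is missing. The top rows are 8 or more days (injection site) and 15 or more days (systemic), followed by a missing row. Section 4.4.1.1.7 derives an ongoing status, which requires at least Grade 1 on the last solicited day and at least Grade 1 afterwards.

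**The concern.** The protocol gives an undated AE a meaning: it is still going on. The SAP does not carry that status into the duration tables. An event that persisted and one whose end was never written down share a row, although a complete start date and a later contact can bound the first from below.

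The effect goes one way: coding a persistent event as missing can lower the longest-duration row but cannot raise it. The missing row may also differ by relationship, because stop dates are actively sought only for related AEs. Duration, or number of days of occurrence, is a planned descriptor of the primary safety endpoints (Protocol 12.1.1.2, SAP 5.1.1.2). In a trial with no hypothesis tests, those tables are the result.

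**Working it through.** The plan states no figure on this point. The check compares the rules and applies the SAP's own formulas.

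**1. Solicited reactions, with no assumption about why the date is missing.** Take a systemic reaction of at least Grade 1 on every day from D0 to D14.
- Days of occurrence in the solicited period (4.4.1.1.5): 15.
- With at least Grade 1 recorded after D14, 4.4.1.1.7 calls it ongoing.
- The formula in 4.4.1.1.6 is (stop date − vaccination date) + days in period − length of period + 1. With the earliest possible stop, D15, this is 15 + 15 − 15 + 1 = 16. Any later stop gives more.
- The category is therefore certain (15 or more days), yet 4.4.1.1.6 reports missing when the stop date is absent.

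For an injection site reaction present on all 8 days from D0 to D7 and ongoing, the minimum is 8 + 8 − 8 + 1 = 9. It belongs in 8 or more days but is again reported as missing.

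**2. Unsolicited AEs truly present at the 6-month contact.** Analysed AEs start between D0 and D28 (SAP 4.4.1.2.3). Taking 6 months as 182 days (assumption), the latest onset after injection 3 gives at least 182 − 28 + 1 = 155 days; with 180 to 183 days the range is 153 to 156. Such an AE is known to exceed 15 days but is tabulated as missing.

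**3. Unsolicited AEs whose persistence nobody checked.** After injection 3, the last visit that records all AEs is Visit 8, at D28 with a window of +14 days, so D28 to D42. The 6-month call asks about SAEs (Protocol 5.1.4). For a non-serious AE starting on D28, the observed length at Visit 8 is between 28 − 28 + 1 = 1 day and 42 − 28 + 1 = 15 days. Subjects who leave early can also have fewer than 15 observed days. An absent stop date does not by itself establish 15 days.

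**4. Possible size, by assumption only.** Let q be the share of dated AEs lasting 15 days or more and m the share of AEs with no stop date. The SAP row shows q(1 − m). If every undated AE really lasted 15 days or more, the share would be q(1 − m) + m. With q = 10%:

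| m | SAP row | If all undated AEs persisted |
|---|---|---|
| 2% | 9.8% | 11.8% |
| 5% | 9.5% | 14.5% |
| 10% | 9.0% | 19.0% |
| 20% | 8.0% | 28.0% |

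The documents give neither q nor m. The right-hand column is a ceiling, and step 3 shows why the truth may lie well below it.

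**The case against.** **The rules do not strictly conflict.** The footnote assigns a status, not a duration or category, and Protocol 12.3.1 allows no replacement of missing safety data. The SAP's refusal to impute follows that, and SAP 5.7 lists 5.3.1.5 among its updated derivations. This stands: a reader might infer a contradiction, but the texts show only a status that was never carried into the tables. It does not justify leaving the gap, because displaying the protocol's own status imputes no date. The SAP also adopts conventions where a field is blank: missing causality counts as related (5.3.1.2), and AEs with missing onset stay in the 28-day tables (4.4.1.2.3).

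**Nothing is hidden.** The AEs remain in every occurrence count and in a visible missing row. Long AEs with a recorded stop date stay in the top row. This also stands. A reader might infer that the longest-lasting AEs are removed from the analysis, but the missing row mixes persistent events with data gaps, partial stop dates and missing start dates.

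**Recoding by last contact date would create false durations.** A short unrelated illness after injection 1 with no recorded end would acquire a duration of more than a year. Given passive collection for unrelated AEs, this is a sound reason against automatic recoding.

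**Ongoing status of solicited reactions is already analysed under 4.4.1.1.7.** That is so, but the duration table still reports as missing a category that the SAP's own derivations establish.

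**HIV-marker SAEs are a poor example.** A reader might think this rule conceals an HIV-marker event that never recovers. Those events come from samples drawn at D28 to D42, so an onset dated after D28 falls outside this table. Persistence is covered by the confirmed indicators (SAP 4.4.1.5.9 and 4.4.1.5.10) and by SAE outcome.

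**Conclusion.** The point holds as a gap in the duration displays. For solicited reactions it rests on the SAP's derivations alone: some reactions whose category is certain are reported as missing. For unsolicited AEs it rests on the protocol's ongoing status having no place in the table, so the row for 15 days or more is a lower bound by an amount that the documents do not let anyone compute.

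The consequence is limited. Duration is one descriptor in a descriptive analysis, and AE occurrence, intensity and relationship counts are unchanged. The documents do not support the view that every undated AE lasted 15 days or more, which would require persistence to have been ascertained in each case. The correction is worth making because it is cheap and lets a reader separate unresolved from unknown.

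**What to change.** 1. **SAP 4.4.1.2.4 and 5.3.1.5.** Add an 'Ongoing at end of study' row, separate from 'Missing', for unsolicited AEs with a complete start date and no stop date. Show it by relationship, and footnote that the status follows the protocol's convention. Assign 15 days or more only when the event was documented as still present at a contact at least 14 days after its start, so that contact date − start date + 1 is at least 14 + 1 = 15. Do not derive the category automatically from the last contact date.
2. **SAP 4.4.1.1.6.** When a reaction is ongoing under 4.4.1.1.7 and its stop date is missing, use the days already counted in the solicited period as a lower bound. A reaction present on all of D0-D14 then goes in 15 or more days, and an injection site reaction present on all of D0-D7 in 8 or more days. Keep 'Missing' where the category cannot be determined.

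The cost is one extra table row and a few lines of programming. No new data are needed: where persistence was not documented, the unsolicited AE simply stays in the ongoing row.
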